## Protocol Synopsis

|                               |   |
|-------------------------------|---|
| Title                         | A randomised study of interferon-free treatment for recently acquired hepatitis C in people who inject drugs and people with HIV coinfection (REACT)  |
| Protocol registration number: | NCT 02625909  |
| Background and rationale      | 
Globally, 3-4 million new hepatitis C virus (HCV) infections are estimated to occur annually (1). People who inject drugs (PWID) represent one of the groups at highest risk of transmitting and acquiring infection with the majority of new (60%) and existing (80%) infections in developed countries occur in this population with HCV antibody prevalence estimated at 67% (60-80%) (2, 3). HIV-positive men-who-have-sex-with-men (MSM) are another high risk group for HCV acquisition.
 
The advent of DAAs has changed the therapeutic landscape for individuals with chronic HCV infection with IFN-free therapy offering high efficacy and tolerability, even in “difficult-to-treat” populations (4-11). Multiple agents in different classes have been approved in Australia by the Therapeutic Goods Administration (TGA), the European Union by the European Medicines Agency (EMA), the US by the Food and Drug Administration (FDA), and in Canada by Health Canada
 
Given the burden of HCV-related disease among PWID and HIV-positive MSM, strategies to enhance HCV assessment, treatment and prevention in these groups are urgently needed. Much of what is known about the timing of treatment initiation, regimen choice and duration of therapy in acute HCV infection comes from small observational studies and randomized controlled trials in selected populations with limited data on treatment in PWID and HIV co-infection. With recent rapid advances in HCV therapeutics, management strategies for acute HCV will evolve rapidly over the next few years.
 
The REACT study will compare the efficacy and safety of sofosbuvir/velpatasvir administered for 6 or 12 weeks in individuals with recent HCV infection. The role and activity of potent DAA regimens in acute HCV infection requires evaluation, with the potential to be given as highly efficacious, short course IFN-sparing regimens, maximising acceptability to patients, encouraging uptake of treatment, limiting further transmission and preventing progression to chronic liver disease.
 |

|                  |  |
|------------------|--|
|                  | Refer to Section 1.0 for complete background and rationale.  |
| Study objectives | 
Hypothesis
Six weeks treatment with sofosbuvir/velpatasvir is non-inferior to twelve weeks treatment with sofosbuvir/velpastavir as assessed by sustained virological response at 12 weeks post treatment in the intention-to-treat population (SVR12).
 
Primary objective
The primary objective is to evaluate the proportion of patients with HCV RNA below the level of quantitation (target not detected [TND] or target detected, not quantifiable [TDnq]) at 12 weeks post end of treatment (SVR12) following sofosbuvir/velpatasvir therapy for 6 weeks (short treatment duration) as compared with 12 weeks (standard treatment duration) in people with recent HCV infection (duration of infection <math>\leq</math>12 months).
 
Secondary objectives
 
 
1 To evaluate the proportion of participants with HCV RNA below the level of quantitation (TND or TDnq) at the end of treatment (ETR), 4 weeks after treatment completion (SVR4) and 24 weeks after treatment completion (SVR24);
 
2 To evaluate the proportion of participants with undetectable HCV RNA through 2 years post treatment;
 
3 To evaluate the levels of adherence, factors associated with suboptimal adherence including HIV status, and the impact of suboptimal adherence on therapeutic response;
 
4 To evaluate the impact of treatment on illicit drug use, injecting behaviour and sexual risk taking behaviour (behavioural survey) during treatment;
 
5 To evaluate safety and tolerability
 
6 To evaluate the change in HIV RNA and CD4 (on-treatment and end of treatment);
 
7 To evaluate the rate and risk factors for reinfection during and up to 2 years following treatment;
 
8 To evaluate the immunological factors associated with treatment induced clearance and reinfection
 
9 To evaluate patient interest and attitudes towards long acting parenteral hepatitis C therapy (Long-Acting Hepatitis C Therapy Questionnaire)
 
 |

|                        |   |
|------------------------|---|
| Participant population | 
A total of 250 participants with recent HCV infection will be enrolled from drug and alcohol clinics, tertiary liver and infectious diseases clinics and community health centres across Australia, Canada, Germany, New Zealand, Switzerland, The Netherlands, the United Kingdom and the United States. The Kirby Institute may close or suspend screening prior to reaching 250 participants in order to manage the total study enrolment numbers.
 
The number of participants with HCV/HIV coinfection enrolled to the study will be capped at 70% (or less than 175 participants) of the total study population. In addition, the number of participants with HCV reinfection enrolled to the study will be capped at 20% (or less than 50 participants) of the total study population.
 
Inclusion Criteria
Subjects must meet all of the following inclusion criteria to be eligible to participate in this study.
 
 
1 Participants have voluntarily signed the informed consent form.
 
2 18 years of age or older.
 
3 Detectable HCV RNA at screening (>10,000 IU/ml), and in the opinion of the investigator is unlikely to demonstrate spontaneous viral clearance
 
4 HCV genotypes 1-6.
 
5 HBsAg negative
 
6 Negative pregnancy test at screening and baseline (females of childbearing potential only).
 
7 Male subjects and female subjects of childbearing potential who engage in heterosexual intercourse must agree to use protocol specified method(s) of contraception
 
8 Medically stable on the basis of physical examination, medical history and vital signs
 
9 Adequate literacy to provide reliable responses to the study questionnaires
 
10 All fertile males and females must be using effective contraception during treatment and during the 30 days after treatment end.
 
11 Recently acquired HCV infection (estimated duration of infection ≤12 months)*
 
 |
|------------------------|---|

|  |   |
|--|---|
|  | 
Recently acquired HCV infection as defined by:
 
A)
 
 
i) First anti-HCV Ab or HCV RNA positive within the previous 6 months and
 
ii) Documented anti-HCV Ab negative within the 12 months prior to anti-HCV antibody positive result
 
 
OR
 
B)
 
 
i) First anti-HCV Ab or HCV RNA positive within the previous 6 months and
 
ii) Acute clinical hepatitis (jaundice or ALT > 10 X ULN) within the previous 6 months prior to first positive HCV antibody or HCV RNA, with no other cause of acute hepatitis identifiable
 
 
OR
 
C) For cases of recent HCV reinfection the following criteria are required:
 
 
i) Documented prior HCV antibody positive with HCV RNA negative on at least 2 occasions 6 months apart
 
 
and
 
 
ii) new HCV RNA positive within the previous 6 months
 
 
*Estimated duration of infection based on midpoint between last antibody negative or HCV RNA and first antibody positive or HCV RNA in the case of seroconversion and 6 weeks prior to date of maximum ALT in the case of acute hepatitis.
 
See Section 3.4 for 'Definitions used to calculate Estimated Date of Infection'.
 
If co-infection with HIV is documented, the subject must meet the following criteria:
 
 
1 Antiretroviral (ARV) untreated for >8 weeks preceding screening visit with CD4 T cell count >500 cells/mm^3
 
 
OR
 |
|--|---|

|  |   |
|--|---|
|  | 
2 On a stable ARV regimen for >8 weeks prior to screening visit, with CD4 T cell count >200 cells/mm^3 and an undetectable plasma HIV RNA level.
 
 
• Suitable ARV include: 
 
○ Nucleos(t)ide reverse transcriptase inhibitors: Tenofovir disoproxil fumarate (TDF), tenofovir alafenamide (TAF), emtricitabine (FTC)
 
○ Non-nucleoside reverse transcriptase inhibitors: Rilpivirine
 
○ Protease inhibitors: Atazanavir, darunavir, lopinavir, ritonavir
 
○ Integrase inhibitors: Dolutegravir, raltegravir, elvitegravir/cobicistat
 
 
 
• Contraindicated ARV include: 
 
○ Efavirenz 
 
▪ 50% reduction in velpatasvir (GS-5816) exposure
 
 
 
○ Didanosine
 
○ Zidovudine
 
○ Tipranavir
 
 
 
 
Other ARV agents may be permissible at the time of study commencement pending further drug-drug interaction studies; please discuss with the Medical Monitor.
 
Exclusion criteria
Subjects who meet any of the exclusion criteria are not to be enrolled in this study.
 
 
1 History of any of the following: 
 
a. Clinically significant illness (other than HCV) or any other major medical disorder that may interfere with the participant treatment, assessment or compliance with the protocol; participants currently under evaluation for a potentially clinically significant illness (other than HCV) are also excluded.
 
b. History of chronic pulmonary disease associated with functional limitation, severe cardiac disease, major organ transplantation or other evidence of severe illness, malignancy, or any other conditions which would make the patient, in the opinion of the investigator, unsuitable for the study
 
c. Solid organ transplant
 
d. Malignancy within 5 years prior to screening, with exception of specific cancers that may have been cured by surgical resection (basal cell skin cancer, etc.). Subjects under evaluation for possible malignancy are also excluded.
 
e. Significant drug allergy (such as anaphylaxis or hepatotoxicity).
 
 
 
2 Subject has a known or documented prior history of cirrhosis
 
 |
|--|---|

|              |  |
|--------------|--|
|              | 
 
3 Subject shows evidence of significant liver disease in addition to hepatitis C, which may include but is not limited to drug- or alcohol-related cirrhosis, autoimmune hepatitis, hemochromatosis, Wilson’s disease, non-alcoholic steatohepatitis (NASH), or primary biliary cirrhosis
 
4 Any of the following lab parameters at screening: 
 
a. Direct bilirubin > 1.5 x ULN
 
b. Platelets < 50,000/<math>\mu</math>L
 
c. Creatinine clearance (<math>CL_{cr}</math>) < 50 mL/min
 
d. Haemoglobin < 10 g/dL
 
e. Albumin < 30g/L
 
f. International Normalised Ratio (INR) >1.5 (unless subject is on a stable anticoagulant regimen or has known coagulopathy)
 
 
 
5 Pregnant or nursing female.
 
6 Use of prohibited concomitant medications as described in section 5.2
 
7 Chronic use of systemically administered immunosuppressive agents (e.g. prednisone equivalent > 10 mg/day)
 
8 Known hypersensitivity to velpatasvir, sofosbuvir or formulation excipients.
 
9 Therapy with any anti-neoplastic or immunomodulatory treatment (including supraphysiologic doses of steroids and radiation) <math>\leq</math>6 months prior to the first dose of study drug.
 
10 Any investigational drug <math>\leq</math>6 weeks prior to the first dose of study drug.
 
11 Previous failure of therapy with sofosbuvir or an NS5A inhibitor prior to the first dose of study drug.
 
12 Ongoing severe psychiatric disease as judged by the treating physician.
 
13 Frequent injecting drug use that is judged by the treating physician to compromise treatment safety.
 
14 Inability or unwillingness to provide informed consent or abide by the requirements of the study.
 
15 Prior enrolment within this study.
 
 |
| Study design | 
This study will be conducted as a phase III randomised, open-label, non-inferiority multicentre international trial.
 
A total of 250 people with recently acquired hepatitis C will be enrolled and randomised.
 
The study consists of a screening phase (-12 to -4 weeks), treatment commencement from baseline, randomisation between week 5 and 6, treatment for another 6 weeks for those randomised to standard therapy (12 weeks of treatment) or end of treatment for those randomised to shortened treatment (6 weeks of treatment). Randomisation will be using blocks and will be stratified by study site and HIV status.
  |

|                           |  |
|---------------------------|--|
|                           | 
All participants will then enter the follow-up phase (96 weeks) to evaluate treatment response and reinfection.
 
Participants who become re-viraemic following an end of treatment response will be followed monthly for six months. After completing the monthly follow-up visits, participants will continue to attend three monthly follow-up visits up to two years. Please see section 7 'Reinfection follow-up' for more details.
   |
| Treatment of participants | 
Participants will receive six or twelve 12 weeks of open-label sofosbuvir/velpatasvir (400mg/100mg daily) in an oral once-daily fixed dose combination. Dose modifications are prohibited.
  |
| Study procedures          | 
All participants will complete screening, on-treatment and post-treatment assessments as outlined in the Schedule of Assessments in Section 6.0.
 
Screening assessments must be completed within 12 weeks prior to baseline. There must be a minimum of 4 weeks between screening and baseline.
 
Following screening, eligible participants will commence treatment at baseline. Between week 5 and week 6, participants will be randomised to the shortened or standard treatment duration. On-treatment visits will be conducted at weeks 1, 2, 4 and 6 (end of treatment for participants on shortened treatment duration), weeks 8 and 10 (for participants on standard treatment duration only). Participants on standard treatment duration will attend end of treatment at week 12.
 
For participants randomised to shortened treatment, follow-up visits will be conducted at week 10 (SVR4), week 18 (SVR12), week 30 (SVR24), week 42 (FU1), week 54 (FU2), week 66 (FU3), week 78 (FU4), week 90 (FU5) and week 102 (Termination).
 
For participants randomised to standard treatment, follow-up visits will be conducted at week 16 (SVR4), week 24 (SVR12), week 36 (SVR24), week 48 (FU1), week 60 (FU2), week 72 (FU3), week 84 (FU4), week 96 (FU5) and week 108 (Termination).
 |

|                   |  |
|-------------------|--|
| 
Statistics
 | 
The primary objective of this trial is to establish the non-inferiority of short duration treatment (6 weeks) to the standard duration treatment (12 weeks).
 
Assuming an expected SVR of 90% in the control arm, 113 participants per arm will be required to give 80% chance that the two sided confidence interval of the difference between regimens has a lower limit greater than -12%.
 
A total of 250 subjects enrolled and randomised will comprise the intention-to-treat (ITT) population and will form the study population for evaluation of the primary and secondary endpoints.
 
Primary endpoint:
 
The primary endpoint is the proportion of participants with HCV RNA below the level of quantitation (target not detected [TND] or target detected, not quantifiable [TDnq]) at 12 weeks post end of treatment (SVR12)
 
Secondary endpoints:
 
 
• Secondary virological endpoints 
 
○ The proportion of participants with: 
 
• ETR defined as HCV RNA below the level of quantitation at end of therapy
 
• SVR 4 defined as HCV RNA below the level of quantitation 4 weeks post therapy
 
• SVR 24 defined as HCV RNA below the level of quantitation 24 weeks post therapy
 
• HCV RNA below the level of quantitation through 2 years post treatment
 
 
 
 
 
 
Results will be stratified by HCV genotype and HIV-coinfection.
 
 
• 80/80 adherence: Defined as the receipt of >80% of scheduled doses for >80% of the scheduled treatment period.
 
• 90/90 adherence: Defined as the receipt of >90% of scheduled doses for >90% of the scheduled treatment period.
 
• 100/100 adherence: Defined as the receipt of 100% of scheduled doses for 100% of the scheduled treatment period.
 
• On-treatment adherence: Calculated by subtracting the number of missed doses from the total number of doses of scheduled treatment and dividing by the total intended therapy duration. This measures the proportion of doses received from the time that treatment was initiated until treatment was discontinued or completed.
 
• Toxicity: Proportion of participants with at least one severe or potentially life threatening (grade 3 or 4) adverse event.
 
 |
|-------------------|--|

|  |  |
|--|--|
|  | 

• Early treatment discontinuation: Discontinuation of therapy prior to the per-protocol planned end of treatment (6 or 12 weeks depending on study arm).

• Resistance associated variants (RAVs): The proportion of treated subjects with development of RAVs following virological relapse or breakthrough.

• Reinfection rate: Rates of HCV reinfection will be calculated using person-time of observation during and up to 48 months following end of treatment.

• Baseline characteristics, on-treatment adherence, risk behaviours and toxicity will be evaluated among subjects withdrawing prior to randomisation.

 |
|--|--|

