**Table 1. Estimated duration of infection calculation rules**

| Category  | Estimated date of HCV infection   |
|---|---|
| Acute clinical HCV                                      | 6 weeks prior to onset of acute clinical symptoms   |
| Acute asymptomatic HCV ALT < 400 IU/L                   | Mid-point between last negative HCV antibody or HCV RNA and first positive HCV antibody or HCV RNA  |
| Acute asymptomatic HCV ALT > 400 IU/L                   | 6 weeks prior to the date of peak ALT unless the estimated date of infection is after the date of first HCV antibody positive test. Then, 6 weeks prior to the date of the first HCV antibody positive test |
| HCV antibody negative and HCV RNA positive at screening | 6 weeks prior to the screening date   |

The estimated date of HCV will then be used to determine the estimated duration of HCV infection.

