MedDRA	Medical Dictionary for Regulatory Activities
MELD	Model for End-Stage Liver Disease
PT	preferred term
Q1	first quartile
Q3	third quartile
SAE	serious adverse event
SAP	statistical analysis plan
SD	standard deviation
SOC	system organ class
SVR	sustained virologic response
SVRx	sustained virologic response x weeks after stopping study drug
TD	target detected
TND	target not detected
ULN	upper limit of normal

STUDY DEFINITIONS

HCV virological suppression is defined as HCV RNA below the lower limit of quantitation (LLOQ) (target not detected [TND] or target detected, not quantifiable [TDnq]).

An *end-of-treatment response (ETR)* is defined as plasma HCV RNA below the LLOQ (TND or TDnq) at the end of treatment.

Sustained virological response at 4 weeks post-treatment (SVR4) is defined as plasma HCV RNA below the LLOQ (TND or TDnq) at 4 weeks post cessation of treatment.

Sustained virological response at 12 weeks post-treatment (SVR12) is defined as plasma HCV RNA below the LLOQ (TND or TDnq) at 12 weeks post cessation of treatment.

Sustained virological response at 24 weeks post-treatment (SVR24) is defined as plasma HCV RNA below the LLOQ (TND or TDnq) at 24 weeks post cessation of treatment.

HCV virologic failure is defined as *non-response* (failure of virological suppression on-treatment with quantifiable HCV RNA at all time points between baseline and end of treatment)

Reinfection is defined by the presence of quantifiable HCV RNA after an ETR and detection of infection with an HCV strain that was distinct from the primary infecting strain (heterologous virus on sequencing of Core-E2 and/or NS5B regions).

Relapse is defined by recurrent viraemia by SVR12 where reinfection is not confirmed.

The *presentation of recent HCV infection* at the time of diagnosis is classified as either *acute clinical* or *asymptomatic infection*. *Acute clinical infection* includes participants with a documented clinical history of symptomatic seroconversion illness (including, but not limited to, the presence of jaundice, nausea/vomiting, abdominal pain, fever and hepatomegaly) and those without clinical symptoms but with a documented peak ALT >10 times the upper limit of normal (ULN) within the 12 months prior to diagnosis. *Asymptomatic infection* includes participants with anti-HCV antibody seroconversion but no acute clinical symptoms or documented peak ALT <10x ULN.

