The *duration of HCV infection* at screening and baseline will be calculated from the estimated date of infection. The *estimated date of clinical infection* is calculated as six weeks before onset of seroconversion illness or six weeks before the first ALT >10x ULN. The *estimated date of asymptomatic infection* is calculated as the midpoint between the last negative anti-HCV antibody or HCV RNA and the first positive anti-HCV antibody or HCV RNA. For participants who were anti-HCV antibody negative and HCV-RNA positive at screening, the estimated date of infection is six weeks before enrolment, regardless of symptom status.

On-treatment adherence will be calculated by subtracting the number of missed doses from the total number of doses prescribed for therapy duration and dividing by the total number of doses prescribed for therapy duration. By pill count and self-reported questionnaire, compliance with sofosbuvir/velpatasvir will be individually calculated at the 80, 90 and 100 adherence levels, defined as receipt of ≥80, ≥90 or 100% of scheduled doses.

STUDY DESIGN AND OBJECTIVES

Study Objectives

Primary objective

The primary objective is to evaluate the proportion of patients with HCV RNA below the level of quantitation (target not detected [TND] or target detected, not quantifiable [TDnq]) at 12 weeks post end of treatment (SVR12) following sofosbuvir/velpatasvir therapy for 6 weeks (short treatment duration) as compared with 12 weeks (standard treatment duration) in people with recent HCV infection (duration of infection ≤ 12 months).

Secondary objectives

- To evaluate the proportion of participants with HCV RNA below the level of quantitation (TND or TDnq) at the end of treatment (ETR), 4 weeks after treatment completion (SVR4) and 24 weeks after treatment completion (SVR24);
- To evaluate the proportion of participants with undetectable HCV RNA through 2 years post treatment;
- To evaluate the levels of adherence, factors associated with suboptimal adherence including HIV status, and the impact of suboptimal adherence on therapeutic response;
- To evaluate the impact of treatment on illicit drug use, injecting behaviour and sexual risk taking behaviour (behavioural survey) during treatment;
- To evaluate safety and tolerability;
- To evaluate the change in HIV RNA and CD4 (on-treatment and end of treatment);
- To evaluate the rate and risk factors for reinfection during and up to 2 years following treatment;

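### Protocol Table 1's override for ALT above 400 IU/L dates an asymptomatic reinfection to the earlier, cleared infection; neither the criterion 11 footnote nor the SAP contains this override

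*Protocol*

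**What the plan says.** Infection dating appears in three places.

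- **Criterion 11 footnote (protocol synopsis and Section 3.2).** The date is the "midpoint between last antibody negative or HCV RNA and first antibody positive or HCV RNA in the case of seroconversion". A separate ALT rule in the same footnote sets it at "6 weeks prior to date of maximum ALT in the case of acute hepatitis". The footnote refers the reader to Section 3.4. The 12-month limit applies to definitions A, B and C alike.
- **Protocol Section 3.4, Table 1.** Symptomatic cases are dated from symptom onset. Asymptomatic cases with ALT below 400 IU/L get a midpoint of antibody or RNA tests. Asymptomatic cases with ALT above 400 IU/L are dated 6 weeks before peak ALT, unless that date falls after the first antibody-positive test: "Then, 6 weeks prior to the date of the first HCV antibody positive test".
- **SAP, Study Definitions.** Clinical infection, which includes symptom-free cases with a peak ALT above 10 times ULN, is dated from the illness or from the first ALT above that threshold. Asymptomatic infection is dated at "the midpoint between the last negative anti-HCV antibody or HCV RNA and the first positive anti-HCV antibody or HCV RNA". The asymptomatic class "includes participants with anti-HCV antibody seroconversion but no acute clinical symptoms".

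Definition C admits reinfections. Its first part requires "Documented prior HCV antibody positive with HCV RNA negative on at least 2 occasions 6 months apart". Its second part, on the current episode, requires a "new HCV RNA positive within the previous 6 months".

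**The concern.** The Table 1 override makes sense for a first infection. A person cannot be antibody positive before being infected, so an ALT-based date later than the first positive antibody test must be moved back. In a reinfection the first positive antibody test belongs to an infection that has since cleared, and moving the date back to it describes the wrong episode.

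Two things are at stake. The first is eligibility. Definition C limits how recent the new positive RNA must be but sets no limit on the gap since the last negative RNA, so the 12-month duration limit is what bounds the age of a reinfection. The override can make that limit reject people whom definition C is written to admit. The second is the SAP's duration variable, which is summarised at baseline (SAP Table 7) and named among the univariate factors for treatment outcome.

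A lesser point concerns wording. The SAP's asymptomatic class presupposes antibody seroconversion, which someone already antibody positive does not undergo. The midpoint rules allow RNA dates but do not say that the tests must come from the current episode.

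**Working it through.** The plan states no figure to reproduce. The check applies each rule to a definition C case. All calendar dates below are assumed for illustration; one month is 30.4375 days.

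**1. When does the override apply?** Take the first antibody-positive test (Ab) to be no later than the first of the two negative RNA results, which are 6 months apart. A current-episode ALT peak comes after the second negative, so it is more than 6 months after Ab. Six months less 6 weeks is still positive, so the ALT-based date always falls after Ab and the override always applies.

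**2. What duration results?** The overridden date is Ab minus 42 days, which is before the documented RNA-negative period.
- Minimum duration: more than 6 + 42/30.4375 = 7.4 months.
- The 12-month limit is exceeded once Ab lies more than 12 − 42/30.4375 = 10.6 months before the date at which duration is assessed.

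The override therefore always dates the wrong episode in such a case. It breaches criterion 11 only when the earlier diagnosis is older than about 10.6 months.

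**3. Illustration.** Antibody negative 1 Jan 2012; first antibody positive 1 Jan 2013; last RNA negative 1 Dec 2017; new RNA positive 1 Apr 2018; peak ALT 15 Apr 2018; screening 1 Jun 2018.

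| Rule | Estimated date | Duration at screening |
|---|---|---|
| Peak ALT − 6 weeks | 4 Mar 2018 | 2.9 months |
| Table 1 override: first antibody positive − 6 weeks | 20 Nov 2012 | 66.3 months |
| Midpoint of last negative and new positive RNA | 30 Jan 2018 | 4.0 months |
| Midpoint using the old antibody tests | 2 Jul 2012 | 71.0 months |

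A second set of dates behaves the same way. With first antibody positive 1 Jan 2012, peak ALT 1 Mar 2017 and screening 15 Mar 2017, the ALT rule gives 18 Jan 2017 (56 days, or 8 weeks). The override gives 20 Nov 2011 (1,942 days / 30.4375 = 63.8 months).

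**4. Does an RNA-based date work?** If the new positive RNA is g months before screening and the gap from the last negative is h months, the duration is g + h/2. The limit holds when h ≤ 2(12 − g): 24, 18 or 12 months for g = 0, 3 or 6. The RNA reading thus gives a usable date and a meaningful limit for definition C.

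**5. The ALT rules side by side.**

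| Source | ALT anchor | Antibody override |
|---|---|---|
| Footnote, synopsis and 3.2 | Maximum ALT, acute hepatitis | No |
| Table 1 | Peak ALT, asymptomatic, above 400 IU/L | Yes |
| SAP | First ALT above 10 times ULN | No |

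The same reinfection can therefore be dated years apart depending on which passage is followed.

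**The case against.** The strongest reply is that the plan already supplies what is needed. The footnote, the Table 1 row for ALT below 400 IU/L and the SAP midpoint all name HCV RNA as an alternative to antibody. Definition C requires the RNA results, and the symptom rules and the footnote's maximum-ALT rule use no antibody test. The footnote limits its midpoint to seroconversion but sends the reader to Section 3.4, where the midpoint row has no such limit. Pairing a recent negative with a positive from years earlier would put the first positive before the last negative, which no one would intend. Dating a new episode to a cleared infection would also defeat definition C.

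Most of this stands. A reader might infer that all the dating rules rest on antibody tests, so that every reinfection is misdated or has no date. The documents do not support that. A reader might also infer that harmonising the protocol with the SAP would leave the main fault in place. It would not if Table 1 were aligned to the SAP, because the SAP has no override; only the class and current-episode wording would remain.

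What the reply does not answer is the row for ALT above 400 IU/L itself. It offers no RNA alternative, its instruction is explicit, and it sits in the table to which the footnote refers.

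**Conclusion.** The point holds for one row of protocol Table 1. For an asymptomatic definition C reinfection with ALT above 400 IU/L, the override dates the earlier infection and can push the duration past 12 months: 66.3 instead of 2.9 months, or 63.8 months instead of 8 weeks, on the assumed dates. It also conflicts with the footnote and the SAP. The result assumes that the rule is applied literally, that the ALT peak is from the current episode, and that the first positive antibody result is no later than the first of the two RNA negatives.

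The number affected is unknown. The caps on reinfection (fewer than 50 in the synopsis and Section 4.1, fewer than 125 in Section 3.1) are outer bounds only, since most dating routes do not pass through this row.

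The consequences are limited to eligibility dating, the baseline duration summary and the univariate duration factor. SAP Table 12 makes its analysis of efficacy factors conditional on a low SVR12. A reader might try to attach a shift in mean duration to the 192-participant analysis. The documents do not support any such figure: the SAP lacks the override, and neither the number of such cases nor the age of the earlier infections is given. The SAP's duration variable would be wrong only if Table 1 dates were carried into it, or if its own midpoint were taken from old-episode tests. The SVR12 comparison of randomised arms does not use the infection date.

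**What to change.** - **Footnote (synopsis and 3.2), Table 1 and SAP Study Definitions:** state that definition C cases are dated from current-episode tests only, using the midpoint of the last negative and first new positive HCV RNA, and current-episode ALT where an ALT rule applies.
- **Table 1, row for ALT above 400 IU/L:** for reinfections, tie the override to the first positive HCV RNA of the current episode, or remove the override so that the row matches the SAP.
- **SAP asymptomatic class:** add that, for reinfection, a new positive HCV RNA takes the place of seroconversion.

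The cost is about one sentence in each place and no new data collection for the midpoint, since definition C already requires the RNA results. If enrolment has ended, the same rule should be used to derive the duration variable and to decide which definition C participants, if any, are listed as breaching criterion 11.
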